9.1. Inclusion Criteria

Patients with diabetic retinopathy, glaucoma or macular degeneration Volunteers with written informed consent form Volunteer must be 18 years or older Healthy individuals without retinal disorders

Document No	TF.01.CIP.01
Issue Date	01.05.2023
Revision No	V.00
Revision Date) ** *

9.2. Exclusion Criteria

Volunteers who do not want to have fundus imaging
Cases that do not comply with fundus photography for any reason
Patients with conjunctival and corneal infections,
People with hereditary or congenital retinal diseases,
People with cataracts,
People with uveitis,
Patients with permanent visual impairment in one or both eyes,
Patients with correction of + 6D and above – 6D,
Pregnant

9.3. Subject Withdrawal and Unfollowing Process and Cessation of Device Use

9.4. Relationship of Research Population with Target Population

This clinical study aims to evaluate the accuracy and reliability of Retinow Al software in diagnosing diabetic retinopathy, glaucoma and macular degeneration diseases. The study population includes individuals over the age of 18 who are suspected or diagnosed with these diseases, as well as healthy individuals with no pathological findings in their retinas.

The target population is individuals diagnosed with diabetic retinopathy, glaucoma and macular degeneration. The study population was selected to represent the target population; thus, the effectiveness of Retinow Al software in diagnosing these diseases can be evaluated under real-world conditions. The clinical characteristics of the study population and its similarity to the target population are important in revealing how effective and reliable the software will be in widespread use. In this way, the performance and general validity of the software will be evaluated through tests with the targeted patient group.

10. Procedures

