2.3. Research Center Information

Name of research center	Address
Ankara Bilkent City Hospital	[name]
	[name]

Note: No service is received from outside the center regarding the research.

3. General Summary of the Clinical Trial

Background	Eye diseases stand out as a major public health problem worldwide and constitute one of the
	leading causes of vision loss. Diseases such as diabetic retinopathy, glaucoma and macular
	degeneration are among the problems that can seriously affect the quality of life and lead to
	vision loss. Therefore, early diagnosis of these diseases is vital for determining effective
	treatment methods and protecting and improving the quality of life of patients.
	In recent years, artificial intelligence (AI) technologies in the field of medicine have offered
	great potential in disease diagnosis and management. Artificial intelligence algorithms,
	especially those used for retinal image analysis, play an important role in the early diagnosis of
	eye diseases and the determination of treatment methods. The use of artificial intelligence in
	the field of ophthalmological clinical research is mostly related to the prediction and diagnosis,
	treatment and interventions, and prevention and management of ophthalmic diseases. In this
	context, ophthalmic imaging and early screening systems supported by artificial intelligence
	technology play an effective role in the diagnosis of diseases such as diabetic retinopathy,
	glaucoma and macular degeneration.
	Diabetes is a major global health problem with an estimated 463 million people living with
	diabetes worldwide. This number is expected to increase to 700 million by 2045 [1]. Diabetic
	retinopathy (DR), a common complication of diabetes, is considered the leading cause of new-
	onset blindness among adults aged 20–74 years [2]. As the prevalence of diabetes continues to
	increase, the global DR patient population is projected to increase to 160 million by 2045 [1].
	Early diagnosis and timely treatment of DR can reduce 95% of blindness from this cause [3].
	Therefore, DR screening programs are recommended for patients with diabetes by the World
	Health Organization [4].
	Glaucoma is characterized by optic disc cupping and visual field distortion, and is the most
	common cause of irreversible blindness, affecting more than 70 million people worldwide [5,7].

Document No	TF.01.CIP.01
Issue Date	01.05.2023
Revision No	V.00
Revision Date	:=:

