The primary objective is to evaluate the capability of Retinow AI software to diagnose diabetic retinopathy, glaucoma, and macular degeneration diseases with high accuracy from fundus photographs. The performance of the software will be compared with the diagnoses made by expert physicians and the accuracy, sensitivity, and specificity metrics will be measured. The hypothesis that Retinow AI can reach 90% accuracy will be tested. In this context, the capability of Retinow AI to consistently identify the same disease symptoms in different fundus images will be evaluated by analyzing false positive and false negative results.

Primary Hypothesis:

It is hypothesized that Retinow AI software can diagnose eye diseases such as diabetic retinopathy, glaucoma, and macular degeneration at an early stage with 90% accuracy from fundus photographs. It is anticipated that the software will be able to achieve sensitivity and specificity rates similar to those of expert physicians in the diagnosis of these diseases.

8. Design of Clinical Trial

This clinical trial was designed based on the evaluation of preclinical studies conducted. This clinical trial is a single-center, observational, prospective and cross-sectional study planned to be conducted at Ankara Bilkent City Hospital to determine the primary endpoints of sensitivity, specificity and accuracy of the Retinow Al device for diabetic retinopathy, glaucoma and macular degeneration diseases.

The clinical trial, clinical trial plan, clinical trial results report will be conducted in accordance with the ethical principles of the Declaration of Helsinki, SS-EN ISO 14155:2020 principles and current national and international regulations governing this clinical trial. A signed Declaration of Helsinki will be obtained from all participants in the clinical trial.

Healthy participants who do not have Diabetic Retinopathy, glaucoma, macular degeneration diseases or any eye disease (no pathological findings in the retina) will be included in the study. Inclusion and exclusion criteria of the participants are specified in section 9.

Methods and tools to be used in the study:

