• A non-mydriatic fundus camera will be used to diagnose diabetic retinopathy, glaucoma and macular degeneration, to analyze the retina of healthy individuals and to enable specialist physicians to diagnose diseases from fundus images. This camera allows detailed visualization of the vessels and retinal structure at the bottom of the eye by taking high-resolution retinal photographs. The cleaning of optical components will be

Document No	TF.01.CIP.01
Issue Date	01.05.2023
Revision No	V.00
Revision Date	N=1

done regularly by hospital staff.

• Retinow AI software: Retinow software will be used by retina specialists to evaluate fundus images and compare results for clinical validation of the Retinow AI device. Retinow AI is an artificial intelligence-based software that diagnoses eye diseases by analyzing fundus images. The computer systems on which the software runs will be checked regularly, virus scans and security updates will be made. The analysis results of the software will be compared periodically with the results of specialist ophthalmologists. Since the latest version of the Retinow AI software will be used, no changes will be made to the software during the clinical study.

The clinical study protocol will be carried out in the following steps:

- 1. Participant Selection: Participants who apply to the retina and glaucoma clinic and meet the study inclusion and exclusion criteria will be determined by the specialist physicians in the study.
- 2. Information and Consent: Participants who meet the eligibility criteria will be provided with detailed information about the study and written informed consent will be obtained from them. The content of the informed consent form is arranged in accordance with the relevant integrity and data protection legislation. In the volunteer information and the informed consent form, the volunteer will be fully informed about how the clinical trial data will be collected, used and published.
- 3. Imaging Directions: Participants will be directed to the fundus imaging room by a specialist doctor for fundus photography. Retinal patients diagnosed with diabetic retinopathy, glaucoma, and macular degeneration will be sent for color fundus photography after the initial diagnosis examination. Similarly, healthy participants with no pathological findings in their retinas will be sent for a control fundus photography.

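### Section 9.4 counts suspected cases in the study population, but the inclusion criteria and the imaging step provide only for diagnosed patients and healthy people

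*Combined protocol and SAP*

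**What the plan says.** **Who is in the study.** Section 9.4 describes the study population as "individuals over the age of 18 who are suspected or diagnosed with these diseases", plus "healthy individuals with no pathological findings in their retinas". It adds that the sample represents the target population and lets the software be evaluated in real-world use.

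**Who may be enrolled.** Section 9.1, and the same list in section 3, has one disease criterion, "Patients with diabetic retinopathy, glaucoma or macular degeneration", and one control criterion, "Healthy individuals without retinal disorders". Suspected disease is not mentioned.

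**Who is imaged.** Step 3 of the section 8 procedure has two streams. For the first: "Retinal patients diagnosed with diabetic retinopathy, glaucoma, and macular degeneration will be sent for color fundus photography after the initial diagnosis examination". The second is healthy participants without pathological retinal findings.

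**What healthy means.** Section 8 speaks of "Healthy participants who do not have Diabetic Retinopathy, glaucoma, macular degeneration diseases or any eye disease (no pathological findings in the retina" (the bracket closes there).

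**What the result is for.** Section 4.2 intends the device for people not previously diagnosed. The primary hypothesis in section 7 concerns early-stage diagnosis. Annex 1 sets a 90% threshold on each of accuracy, sensitivity and specificity, for all the diseases.

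**The concern.** Sensitivity and specificity depend on case mix. A classifier usually does best on clear disease against clean controls and worst on equivocal eyes. Whether suspected cases are enrolled is therefore part of what is being estimated, and the plan answers the question in two ways.

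A site working from 9.1 and step 3 would assemble diagnosed patients and healthy controls. A report written from 9.4 would describe suspected and diagnosed people and claim real-world performance. The gap bears on the device's purpose, since both the intended use and the primary hypothesis concern disease not yet established. It also bears on the verdict, because the pass rule is a fixed 90% threshold and a more clear-cut sample makes it easier to reach.

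**Working it through.** **1. The population statements side by side**

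| Place | Disease side | Suspected cases | Control side |
|---|---|---|---|
| 4.2 Intended use | not previously diagnosed | implied | – |
| 4.8 | people presenting for an examination to detect the diseases | implied | – |
| 8, design text | – | – | no target disease and no eye disease, glossed as no pathological retinal findings |
| 8, step 3 | diagnosed at the initial examination | not mentioned | no pathological retinal findings |
| 9.1 and 3 | patients with a target disease | not mentioned | healthy, no retinal disorder |
| 9.4, study population | suspected or diagnosed | **included** | no pathological retinal findings |
| 9.4, target population | diagnosed | not mentioned | – |

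Only 9.4's study-population sentence admits suspects expressly, and 4.8 leans the same way. The two operative texts, 9.1 and step 3, have no such category. Section 9.4 is also uneven within itself, since its target population is diagnosed people only.

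**2. What follows for a person still equivocal after the initial examination.** This person is not clearly a patient with the disease under 9.1 and has not been diagnosed for step 3. If the finding is a suspicious one, the person does not clearly meet the control description either. A literal reading leaves no route in. A person suspected at presentation whose status is settled at that examination does have a route, as a patient or as a control.

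**3. How far equivocal eyes are lost.** Section 8 has both eyes of each participant photographed. Annex 1 computes the measures on eyes and takes the majority of three experts as the truth. Early disease and less-affected fellow eyes of enrolled patients therefore stay in the analysis. Equivocal eyes would be fewer, but not absent.

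**4. Figures.** The plan's total reproduces: 3 diseases × 305 = 915. Nothing in this point changes it.

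The documents give neither the share of equivocal cases nor the accuracy in them. Purely to show why case mix matters near a 90% threshold, let *f* be the share of equivocal cases among true positives:

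overall sensitivity = (1 − f) × Se(clear) + f × Se(equivocal)

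The assumed ranges, not taken from the documents, are Se(clear) 0.93 to 0.95 and Se(equivocal) 0.60 to 0.80.

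| f | Lowest | Highest |
|---|---|---|
| 0 | 0.930 | 0.950 |
| 0.10 | 0.9×0.93 + 0.1×0.60 = 0.897 | 0.9×0.95 + 0.1×0.80 = 0.935 |
| 0.20 | 0.8×0.93 + 0.2×0.60 = 0.864 | 0.8×0.95 + 0.2×0.80 = 0.920 |
| 0.30 | 0.7×0.93 + 0.3×0.60 = 0.831 | 0.7×0.95 + 0.3×0.80 = 0.905 |

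The share at which the value falls to 0.90 is f = (Se(clear) − 0.90) / (Se(clear) − Se(equivocal)). That is 0.03/0.33 = 9% at one end and 0.05/0.15 = 33% at the other. The same formula serves for specificity. Depending on the assumptions, the mix may or may not decide the verdict.

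**5. The definition of healthy.** Section 8 puts a wide meaning (no eye disease) and a narrow one (no retinal findings) in one sentence. Section 9.1 uses a third wording. The 9.2 exclusions (cataract, uveitis, corneal and conjunctival infection, and others) narrow the practical difference without closing it. None of the wordings says whether the optic disc is covered, although section 3 describes glaucoma by its optic disc changes.

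**The case against.** The strongest reply is that 'suspected' in 9.4 may only describe people on arrival. They are then examined, classed as diagnosed or healthy, and photographed. On that reading 9.4, 4.8 and step 3 can coexist. This has force and rules out one inference a reader might draw, that borderline people are turned away. No sentence says so, and 9.1 does not demand a firm or definite diagnosis. What remains is that the plan does not say what happens when the examination leaves the matter open. Some headings, such as 9.3 and 10.1, carry no text in the copy read, so further recruitment detail cannot be ruled out.

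Three other stronger readings also fail:

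- **Section 8 bars every eye disease in controls.** This stops before the sentence's own bracket, which narrows it to retinal findings and agrees with 9.4 and step 3. Section 8 is ambiguous rather than plainly wider.
- **A person with optic disc disease is a valid control under 9.1.** Step 3 counts glaucoma patients among retinal patients, so the plan's use of 'retinal disorders' may well cover glaucoma. The criterion also begins with the word healthy.
- **All equivocal eyes leave the analysis, turning a failure into a pass.** The first part is answered by imaging both eyes and by the expert majority. The second rests wholly on assumed accuracies: with 95% in clear and 80% in equivocal cases, a 30% share still gives 90.5%.

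**Conclusion.** The contradiction on suspected cases stands and should be resolved. Section 9.4 includes them, while the texts a site would apply provide only for diagnosed patients and healthy people. Followed literally, the operative texts yield a sample closer to clear cases against clean controls than 9.4 describes, and further from the undiagnosed users in section 4.2.

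The direction of the effect, towards higher observed sensitivity and specificity, rests on the ordinary assumption that equivocal eyes are harder to classify. The size cannot be derived from the documents, and the illustrative figures show only that case mix could matter at a 90% threshold. The varying definition of healthy is a secondary wording point.

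**What to change.** Choose one of two routes.

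1. **Enrol suspected cases.** Add to 9.1 and section 3 a criterion for people attending with suspected diabetic retinopathy, glaucoma or macular degeneration, and add them to step 3 as a third stream. State in Annex 1 that the three-expert majority assigns each eye's status, whatever the person's label at enrolment.
2. **Do not enrol them.** Delete the reference to suspected cases and the real-world claim from 9.4, and limit the study conclusion to diagnosed cases versus healthy controls.

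The first route fits the intended use better.

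Under either route, use one definition of healthy in sections 3, 8 (including step 3), 9.1 and 9.4. It should keep the requirement of no pathological retinal findings and state whether the optic disc is covered. Bring 4.8 and the target-population sentence of 9.4 into line.

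**Cost.** The second route needs wording only. The first also draws on people already attending the clinic and on the expert grading already planned. Its downsides are that observed accuracy may be lower and that the split of positives and negatives within each 305 becomes less predictable, so that split should be monitored.

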4.2. Intended Use

Retinow AI is a cloud and artificial intelligence based retinal scanning and identification system. Retinow AI is used to analyze diabetic retinopathy (DR), age-related macular degeneration (AMD) and glaucoma diseases of patients who have not previously been diagnosed with the disease, in a short time, through fundus images, thanks to artificial intelligence. Retinow AI presents a report to the user through the system without the need for any expert opinion. It works as a decision support mechanism for specialist or non-specialist physicians. It detects pathological areas in the retina and automatically detects problems.

Document No	TF.01.CIP.01
Issue Date	01.05.2023
Revision No	V.00
Revision Date	:=:

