4.8. Target Patient Population and Research Population

There is no restriction on the gender and physical structure of the patient where our device will be used. Our device should be used for 3 identified diseases: Macular degeneration, diabetic retinopathy and glaucoma. Retinow Al software should be used on patients who are 18 years old or older. The target patient population and study population were persons aged eighteen years and over who presented to an ophthalmologist for an eye examination to detect diabetic retinopathy, macular degeneration, and glaucoma.

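### Section 9.4 claims real-world representativeness for diagnosed people, while the device is intended for undiagnosed people, whom the planned data cannot identify

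*Combined protocol and SAP*

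**What the plan says.** The protocol describes the relevant population in several places.

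- Section 4.2 (Intended Use) says that the software is for "patients who have not previously been diagnosed with the disease".
- Section 4.8 gives the target and the study population together, as "persons aged eighteen years and over who presented to an ophthalmologist for an eye examination to detect diabetic retinopathy, macular degeneration, and glaucoma".
- Section 9.4 says: "The target population is individuals diagnosed with diabetic retinopathy, glaucoma and macular degeneration". It continues: "The study population was selected to represent the target population", and concludes that the software's effectiveness "can be evaluated under real-world conditions".
- Section 9.4 also describes the study population, as "individuals over the age of 18 who are suspected or diagnosed with these diseases, as well as healthy individuals with no pathological findings".
- Section 9.1 admits on the disease side "Patients with diabetic retinopathy, glaucoma or macular degeneration". On the other side it admits healthy people with no retinal disorder.

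Section 8 recruits from a retina and glaucoma clinic. Patients go for photography once the first diagnostic examination is done, and controls go once no retinal pathology has been found. The controls are described as free of the three diseases and of every other eye disease. The primary hypothesis in section 7 is about diagnosis at an early stage. The SAP (Annex 1) sets pass marks of 90% for accuracy, sensitivity and specificity, and lists age and gender as the baseline data.

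**The concern.** Section 9.4 makes a claim about whom the results apply to, and that claim does not match the stated use of the device. Someone who already carries a diagnosis is outside the intended use in section 4.2, yet that is the person 9.4 names as the target.

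The mismatch matters because sensitivity and specificity depend on which cases and which controls are enrolled. Established cases may show clearer signs than cases found for the first time, and people with no eye disease are easier to call negative than people with other findings. If so, both measures would look better in this sample than in people coming for screening. The study rationale in section 3 is screening, so a pass on the 90% marks would naturally be read as screening performance. Nothing in the SAP would let anyone test that reading.

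**Working it through.** The plan gives no figure for this point, so the first three steps compare text. The later steps are illustrations.

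**1. Whose performance is claimed?**

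| Section | Population | Fits undiagnosed use? |
|---|---|---|
| 4.2 | No prior diagnosis | Yes |
| 4.8 | Attending so that disease can be detected | Yes, can be undiagnosed |
| 9.4, target | Diagnosed | No |
| 9.4, study | Suspected, diagnosed or healthy | Partly |
| 9.1 | Has a disease, or healthy | Not stated |

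Sections 4.2 and 4.8 can be read together. The target sentence in 9.4 is the one out of line.

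**2. Who is enrolled?** Under section 8, disease status is settled before the photograph is taken. No inclusion criterion or procedure step names suspected people as a category. Patients first diagnosed at that visit can enter, and so can patients diagnosed earlier. The documents do not give the proportions.

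**3. Could the data separate them?** The SAP lists age and gender only. It lists no prior-diagnosis field and no analysis by that status.

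**4. What does a pooled pass imply?** Let k be the share of known cases, S_known and S_new the two sensitivities, and S the pooled value:

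S = k × S_known + (1 − k) × S_new, so S_new = (S − k × S_known) / (1 − k).

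Only the 90% pass mark comes from the documents; k, S_known and S_new are assumptions. With k = 0.7, S_known = 0.96 and S_new = 0.78:

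S = 0.7 × 0.96 + 0.3 × 0.78 = 0.672 + 0.234 = 0.906.

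Setting S = 0.90 and varying S_known from the pass mark to its ceiling of 1.00 gives these values of S_new:

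| S_known | k = 0.5 | k = 0.7 | k = 0.8 |
|---|---|---|---|
| 0.90 | 0.90 | 0.90 | 0.90 |
| 0.96 | 0.84 | 0.76 | 0.66 |
| 1.00 | 0.80 | 0.67 | 0.50 |

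For example, (0.90 − 0.7 × 0.96) / 0.3 = 0.228 / 0.3 = 0.76. If known cases did worse than 0.90, S_new would exceed 0.90. A pooled 90% alone therefore fixes neither the size nor the direction of the difference.

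**5. Specificity.** Assume 0.95 in controls free of eye disease, 0.60 to 0.80 in people with other eye findings, and a 30% share of the latter in use. Overall specificity is then 0.7 × 0.95 + 0.3 × 0.60 = 0.845, up to 0.7 × 0.95 + 0.3 × 0.80 = 0.905. These values are also assumptions.

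**6. Precision of a newly detected subgroup.** The plan has 305 people per disease, and 3 × 305 = 915 reproduces its total. Healthy participants are enrolled too, and the text does not say whether they count within the 305. Taking all 305 as cases is therefore a favourable assumption. With one result per person and sensitivity 0.90, the 95% half-width is 1.96 × √(0.90 × 0.10 / n):

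- all cases, n = 305: 3.4 points
- 50% newly detected, n ≈ 152: 4.8 points
- 30%, n ≈ 92: 6.1 points
- 20%, n = 61: 7.5 points

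**The case against.** The best defence is that the documents do not restrict enrolment to known cases. Section 9.4 itself mentions suspected people, section 4.8 describes the study population as attending for detection, and section 9.1 requires the disease but not a previous diagnosis. The first diagnostic examination in section 8 may be the visit at which disease is first found. All of this stands. A reader might infer that the intended-use population is not studied at all, or that the protocol gives three incompatible target populations. The text supports neither reading: newly diagnosed people may be enrolled, and 4.2 and 4.8 are compatible.

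Some of the control selection also matches the labelled use. Cataract, uveitis, hereditary or congenital retinal disease, and conjunctival or corneal infection are both exclusions and contraindications, so leaving them out of the controls creates no mismatch. Eye findings outside that list remain a fair point.

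Prior diagnosis is an imperfect proxy for disease stage: a new case can be advanced and a known one mild. That limits what the subgroup can show, but 4.2 defines the use by prior diagnosis, so that status still has to be known.

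Finally, the stratum values are assumed, and some of the protocol text is not available, including any content under section 10.3 on factors that may compromise the results. I draw nothing from its absence.

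None of this supports the claims in 9.4. If newly detected cases are enrolled, the plan still cannot tell them from known ones.

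**Conclusion.** The concern holds in a limited form. The target population in 9.4 conflicts with 4.2 and does not match 4.8. Its statements on representativeness and real-world evaluation are not supported by a design that sorts participants into diagnosed cases and controls without eye disease before the software is applied. The share of newly detected cases is unspecified and, on the listed baseline data, cannot be identified. A pass on the 90% criteria would therefore not show performance in intended-use patients.

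A reader might go further and infer that the reported accuracy will be inflated by a known amount. The documents do not support that. They give no sensitivity or specificity by prior diagnosis or by type of control, so the size of any bias cannot be computed, and its direction is only a reasoned expectation. The 96%, 78% and 70/30 values are illustrative. The study can run as designed, but its stated conclusion needs correcting.

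**What to change.** 1. Rewrite the target population in 9.4 so that it agrees with 4.2 and 4.8.
2. Record at enrolment, for each case, whether the disease was already diagnosed or first found at this visit.
3. Pre-specify in the SAP, for each disease, sensitivity with a 95% CI separately for newly detected and known cases. Use the newly detected figure to support any intended-use claim about sensitivity.
4. Remove from 9.4 the statements quoted above as "The study population was selected to represent the target population" and "can be evaluated under real-world conditions".
5. Limit the conclusion to diagnosed cases versus healthy controls. Specificity stays under that limit whatever the subgroup shows, because the new field describes cases and does nothing for the choice of controls.

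This takes one yes/no field, one stratified table per disease and a wording change. Recruitment and sample size stay as they are. The price is a narrower claim and a possibly wide interval for newly detected cases. If few are enrolled, the subgroup will support little, and the report should say so.
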